2.3.2 KNOWN POTENTIAL BENEFITS

gammaCore has been successfully studied for the acute and preventive treatment of cluster and migraine headache.(19) It has been proven to decrease headache intensity, and prevent migraine attacks. To this point it has not been studied in patients with headache due to SAH. Given the shared pathophysiology (inflammation, cortical spread depression) and the potential of deactivating the nociceptive center, nVNS could potentially alleviate SAH related headache, decreasing the usage of opiates and steroids and thereby decreasing their side effects. This could potentially decrease the ICU and hospital length of stay, decrease the readmission rate from headache due to SAH, decrease the outpatient usage of opiates and prevent opiate dependency.

In addition, nVNS could also provide neuroprotection against stroke, one of the most feared complication in a-SAH. Stroke in a-SAH is thought to be due to vasospasm of blood vessels caused by inflammation and cortical spreading depression leading to ischemia. In animal model, noninvasive VNS has been shown to significantly reduce CSD.(11) In addition, nVNS has anti-inflammatory properties. Experimental animal studies have shown that VNS has the potential of improving outcome in critical illnesses through its anti-inflammatory effects which could potentially extend to sepsis, intracranial hemorrhage, ventilator related lung injury, postoperative cognitive dysfunction, myocardial ischemia and reperfusion injury. One of the postulated mechanisms, is that it regulates α 7nAChR which regulates inflammation.(23) Animal studies have shown that stimulating the α 7nACh decreases inflammatory markers.(24) Through inhibiting CSD and controlling inflammation, nVNS could potentially prevent secondary brain injury (strokes and DCI) seen in a-SAH patients.

Studies have also shown that VNS enhances neuroplasticity, which could fasten recovery. Animal studies on intracranial hemorrhage showed that VNS improves functional recovery.(25) Multiple ongoing studies are evaluating the beneficial effects of VNS in improving functional recovery during rehabilitation of patients with strokes.(22) nVNS could potentially help recovery from SAH.

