6.1.2 DOSING AND ADMINISTRATION

Two-two minute transcutaneous stimulations will be administered every 5 hours (approximately 6:30AM, 11:30 AM, 4:30 PM and 9:30 PM) with no relation to meals. Some patients might miss few stimulations as they might be getting a procedure, have unstable vital signs, or refuse the stimulation, amongst other reasons that might make stimulation not feasible. If vital signs are stable (HR > 60 beats/minute, and SBP> 100 mmHg and MAP> 60 mmhg and saturation > 90% on room, nasal cannula or face mask,), nVNS or Sham will be initiated. We will start by placing gel on the skin of the neck, the device will be placed in direct contact with the gel and the skin. The stimulation will be performed by the patient, with assistance from an IRB approved personnel if the patient is uncomfortable performing it. The stimulation intensity will be increased as directed by the gammaCore pamphlet. Patients will be informed that they may or may not feel a tingling sensation with the investigational device and the sham device. Two 2 minutes stimulation will be provided. Tolerance will be assessed during and directly after stimulation and every 5 hours afterwards as directed by the intensivist on call.

If a digital subtraction angiography is being performed for vasospasm, nVNS will be delivered to assess its effect on cerebral vasospasm.

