7 STUDY INTERVENTION DISCONTINUATION AND PARTICIPANT DISCONTINUATION/WITHDRAWAL

7.1 DISCONTINUATION OF STUDY INTERVENTION

The study intervention will be held during procedure days, or if the participant gets intubated, or is in shock (cardiogenic, distributive or septic). During non-procedure days, or once extubated and stabilized and participant becomes alert the study intervention can be resumed.

In addition, as stated earlier, if HR< 60 beats/min, SBP<100 mm HG, or MAP< 60 mm HG and oxygen saturation < 90 %, the intervention will be postponed.

If hemodynamic instability or unstable arrhythmia occur during the VNS, and is thought to be due to the VNS by the investigator, the participant will be discontinued from the study procedure, however, will be followed until discharge from the hospital.

If a clinically significant finding is identified (including, but not limited to changes from baseline) after enrollment, the investigator or qualified designee will determine if any change in participant management is needed. Any new clinically relevant finding will be reported as an adverse event (AE).

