9.3 POPULATIONS FOR ANALYSES

Participants who received at least 1 stimulation will be included in the Intent To Treat (ITT) population. Opiate usage and pain intensity during the days of procedures in which patients are intubated and unconscious will be excluded from the analysis. The days of EDV weaning will be noted, given that hydrocephalus can cause headache due to high ICP. A modified Intent-to-treat (mITT) population inclusive of all subjects who treat at least 7 days with at least 3 stimulations of the study device; and a per-protocol (PP) population of people who are compliant with the treatment regimen for the duration of the study will be analyzed.

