- Rate of side effects:
 - o presence of intolerable pain at the stimulation site,
 - o skin irritation,
 - o nasopharyngitis,
 - o hoarseness,
 - o dysgeusia,
 - o shortness of breath,

Outcome measures

Primary efficacy variable:

The daily morphine equivalency dosage by visit

Secondary efficacy variables:

- total overall morphine equivalence dosage
- mean daily headache intensity during by visit
- cytokines levels
- blood brain permeability markers in the blood and/or CSF before and after stimulation
- blood brain barrier integrity

Exploratory variables:

(Stroke, vasospasm, DCI, seizure, and central fever)

- The presence of DCI,
- Transcranial doppler velocity,
- The number of days with central fever,
- Incidence of seizures)
- severity of cerebral vasospasm during DSA

Safety variables:

Opiate related adverse events

- urinary retention,
- constipation,
- sedation,
- nausea,
- vomiting and
- pruritis
- Occurrence of Adverse Events (AEs)/Serious Adverse Events (SAEs)

Rate of side effects: presence of intolerable pain at the stimulation site,

- skin irritation,
- nasopharyngitis,
- hoarseness,
- dysgeusia,

- shortness of breath,
- Vital Signs (weight, BMI, SBP, DBP, and pulse rate are collected at each day)

Statistical considerations

Sample size determination

There are no statistical hypotheses in this study, and therefore there is no sample size justification for this study. This is a feasibility pilot study that will allow us to better calculate the sample size for a large, randomized control study comparing VNS to sham device.

General approach:

- Baseline is defined as the value measured at visit 1 (Day 1). Endpoint is defined as last observed value during visit 14 (Day 14).
- Missing efficacy. Two statistical approaches to handling missing data will be performed in this study.
 - The primary analysis will be a repeated measures analysis of the primary efficacy endpoint. Estimates have been shown to be unbiased when the missing data are missing completely at random and when there is ignorable nonrandom missing data.
 - A secondary analysis will utilize an LOCF analysis
- All statistical tests for treatment difference will be 2-sided and conducted at the 0.05 level of significance.

Analysis populations

The following analysis sets will be used for the statistical analysis and presentation of data:

- ITT: All randomized participants will be included in the Intent To Treat (ITT) population.

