- Modified ITT (mITT): A modified Intent-to-treat (mITT) population inclusive of all ITT subjects who are treated at least 7 days with at least 3 stimulations of the study device.
- The Per Protocol Set (PPS): Patients who are compliant with the treatment regimen for the duration of the study will be analyzed.
- The safety set will consist of all randomized patients who received at least one stimulation.

The mITT is considered as the primary analysis dataset and will be used for all primary and secondary efficacy analyses. The primary efficacy analyses will be repeated using the PP set. Any discrepancy between the results from the mITT and the PP will be analyzed and discussed.

The secondary variables will be analyzed based on mITT only.

Baseline data and safety analysis will be based on the safety set.

Patient characteristics

In general, data will be summarized by means of summary statistics. Continuous data will be presented with the number of observations, mean value, standard deviation, minimum, median and maximum value. The mean, standard deviation and median will be given with one decimal more than the original values. When applicable, values at each visit, as well as changes from baseline, will be summarized.

Categorical data will be presented as counts and percentages. The data will be presented for each treatment group by visit.

Patient demographics and vital signs will be summarized for all randomized patients. For each of the variables, the treatment group difference will be examined using T-test for continuous variables, and Fisher's exact test for categorical variables.

Efficacy Analysis

The primary analysis of the primary efficacy variable will be based on the mITT population set.

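### The primary efficacy set is chosen by events after randomisation, and no efficacy analysis uses all randomised patients

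*SAP*

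**What the plan says.** The SAP (Analysis populations) defines four sets.

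- **ITT:** "All randomized participants will be included in the Intent To Treat (ITT) population".
- **mITT:** those ITT subjects "who are treated at least 7 days with at least 3 stimulations of the study device".
- **Per-protocol (PPS):** patients compliant with the regimen throughout the study.
- **Safety:** randomised patients with at least one stimulation.

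It then assigns them: "The mITT is considered as the primary analysis dataset and will be used for all primary and secondary efficacy analyses". The primary analysis is repeated on the PPS, and "The secondary variables will be analyzed based on mITT only". The sensitivity analyses are the PPS repeat and an LOCF run whose set is not named. All randomised patients appear only in the summary of demographics and vital signs.

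Protocol 9.3 defines ITT differently: "Participants who received at least 1 stimulation will be included in the Intent To Treat (ITT) population". It lists mITT and per-protocol sets as well and names none of the three as primary. The protocol (Version 6, January 2023) is later than the SAP (May 2022), but only the SAP chooses a primary set.

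**The concern.** Randomisation protects a comparison of the groups as randomised. A set that needs 7 treated days is known only afterwards, and the protocol lists many ways to miss it:

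- discharge before the treatment period ends (5.5);
- missed sessions: "Some patients might miss few stimulations as they might be getting a procedure, have unstable vital signs, or refuse the stimulation" (6.1.2);
- holds: "The study intervention will be held during procedure days, or if the participant gets intubated, or is in shock" (7.1);
- stopping for instability attributed to the device (7.1);
- withdrawal, including for non-compliance or for more than 3 consecutive days without the intervention (7.2).

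Some of these could depend on the arm. On the effect of less opiate and steroid use, protocol 2.3.2 says: "This could potentially decrease the ICU and hospital length of stay". If the device works in that way, responders may leave hospital early and drop out of the set meant to show the benefit. Stopping for device-attributed instability would act for a different reason. The sign of any bias therefore cannot be predicted.

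The SAP tests at two-sided 0.05, and the pilot is meant to help size a larger trial, so a selected estimate would be carried forward. The planned comparison of mITT with PPS sets one post-randomisation selection against another, so agreement between them would not be reassuring.

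**Working it through.** **1. Which set gets which analysis (SAP).**

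| Analysis | Set |
|---|---|
| Primary MMRM | mITT |
| Repeat of primary | PPS |
| LOCF | not named; mITT if the general sentence applies |
| Secondary variables | mITT only |
| Demographics, vital signs | all randomised |

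ITT receives no primary, secondary or sensitivity efficacy analysis. MMRM and LOCF deal with missing days among patients kept in a set. Neither recovers a patient who has been removed from it.

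**2. Size of a possible bias.** The plan has no figure to reproduce: it states no power, SD, effect size or exclusion rate. Inputs from the documents are about 40 patients, equal allocation (20 per arm) and two-sided 0.05. Everything else in this step is assumed.

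Let the outcome be Y ~ N(0,1) in both arms, so there is no true effect. Let Z = ρY + √(1−ρ²)·e, and exclude a patient when Z exceeds its (1−p) quantile q. Then

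bias = −ρ × [φ(q_active)/(1−p_active) − φ(q_sham)/(1−p_sham)].

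φ(q)/(1−p) is 0.350 at p = 0.2, 0.644 at 0.4 and 0.798 at 0.5.

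- 40% v 20%: 0.644 − 0.350 = 0.294. Times ρ = 0.3, 0.6, 0.9 this gives 0.088, 0.176, 0.265 SD.
- 50% v 20%: 0.798 − 0.350 = 0.448. This gives 0.134, 0.269, 0.403 SD.

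In this set-up high opioid users leave, more of them from the active arm, so the bias favours the device. If low users leave instead, the sign reverses.

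Simulated type I error (t-test standing in for the MMRM, 12,000 trials per cell):

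| Exclusion, active v sham | ρ = 0.3 | ρ = 0.6 | ρ = 0.9 |
|---|---|---|---|
| 20% v 20% | 0.048 | 0.049 | 0.050 |
| 40% v 20% | 0.056 | 0.077 | 0.132 |
| 50% v 20% | 0.064 | 0.105 | 0.230 |

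With all randomised patients observed, it is 0.049 to 0.051.

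*Baseline adjustment* (baseline–outcome correlation 0.5 to 0.7) reduces the bias but does not remove it. At 40% v 20% the bias is 0.04 to 0.22 SD, with type I error 0.05 to 0.12. At 50% v 20% it is 0.07 to 0.33 SD, with 0.06 to 0.20.

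*Equal rates, opposite reasons.* If low users leave one arm and high users leave the other (correlation 0.5), exclusion of 10%, 20% and 30% in each arm gives bias of 0.19, 0.35 and 0.50 SD and type I error of 9.0%, 17.4% and 27.1%. Equal exclusion counts are therefore no safeguard.

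**3. Precision.** The unadjusted 95% half-width is t(0.975, 2n−2) × √(2/n): 0.64 SD at 20 per arm, 0.72 at 16 and 0.85 at 12.

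**4. Can everyone reach 7 days?** Enrolment runs to day 5 after aneurysm treatment (protocol 4.1). The end of the window is stated in several ways.

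- Synopsis and 5.5, ending on day 10: 10 − 5 + 1 = 6 days. Ending on day 11: 11 − 5 + 1 = 7 days, with none missed.
- Flow figure in 8.2, ending on day 10 after ictus: if treatment came 3 days after ictus (assumed) and enrolment 5 days later, 10 − 8 + 1 = 3 days.
- Protocol 4.1 and 8.1 allow up to 10 days of stimulation or treatment, and the SAP analyses to Day 14.

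On some readings an eligible late enrollee cannot enter the primary set. That costs numbers; it does not by itself cause bias.

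**The case against.** **All-randomised analysis may not help with early discharge.** Data collection ends at discharge, while the SAP's primary contrast is at Day 14. In the single-outcome model above, a discharged patient with no outcome is lost from both sets. This is a fair limit on the 0.05 benchmark, which assumes everyone is observed. It does not carry over to the planned MMRM, which uses the days before discharge. A further null simulation assumed 40% v 20% discharge after day 4, driven by opioid level. The mITT bias was 0.17 to 0.26 SD. ITT bias was at most 0.02 SD when discharge depended on observed doses, and 0.02 to 0.05 SD when it depended on unobserved ones.

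**The illustrated rates are assumed, and the protocol's route to a shorter stay runs through lower opioid use.** Both points stand. Under a strict null on opioid dose, that route gives no differential discharge. If the device works, it would tend to bias against the device. Blinding also makes differential refusal less likely. The figures show what selection could do; they do not forecast it.

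**The rule is ambiguous.** Three stimulations could be per day or in total. With four sessions a day of two stimulations each, the in-total reading excludes few patients for missed sessions. The 7-day requirement remains on either reading.

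**It is a pilot with no stated hypotheses.** This lowers the stakes. The SAP nevertheless plans significance tests at 0.05, and the result is meant to inform the next trial.

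**Conclusion.** The concern holds and should be fixed before analysis. From the text alone, the main efficacy result is not a comparison of the groups as randomised, and no planned efficacy analysis would show whether that mattered. Bias is possible, not certain. It is close to nil if patients leave both arms at the same rate for the same reasons, and roughly 0.1 to 0.4 SD under the assumed unequal rates without baseline adjustment. It reaches 0.5 SD at 30% exclusion per arm for opposite reasons. These sizes rest on assumed exclusion rates and correlations and on single-outcome tests standing in for the MMRM. The firm statement covers primary and secondary efficacy, because the SAP names no set for the exploratory variables.

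**What to change.** 1. In the SAP, make ITT (all randomised, analysed as assigned, all observed days in the study window, by the planned MMRM) the primary set for the primary endpoint. Use ITT for the secondary efficacy analyses too. Keep mITT and PPS as supportive, and report exclusions from each by arm and reason.
2. Align the ITT definition in protocol 9.3 with the SAP's.
3. In protocol 7.2, state that opioid, pain and adverse-event data continue to be extracted after the device is stopped, through the study window or hospital discharge, unless consent is withdrawn. State also that replacing an untreated subject does not remove a randomised subject from ITT.
4. For the supportive mITT, say whether the three stimulations are per day or in total.
5. Reconcile the passages on the study window so that both documents use one.

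The cost is wording. Doses and pain scores are already in the medical record, collection already runs to discharge (protocol 4.4), and the MMRM accepts incomplete series. There are two downsides: non-adherence may dilute the ITT estimate somewhat, and patients discharged early still contribute shorter series, so the analysis continues to rely on the missing-data assumption for those days.

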6.3 MEASURES TO MINIMIZE BIAS: RANDOMIZATION AND BLINDING

To minimize bias, this will be a randomized controlled trial. Patients will be randomized using variable block design, assigning patients 1:1 to the treatement group n-VNS and sham group, with concealment of allocation. Participants and the provider assessing the pain scale, providing the pain killers and assessing for adverse events will be blinded.

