8 STUDY ASSESSMENTS AND PROCEDURES

8.1 EFFICACY ASSESSMENTS

Per standard of care, patients presenting with signs of SAH like acute severe headache, will get a diagnostic head CT which confirms blood in the subarachnoid space. If patients have symptomatic hydrocephalus (altered mental status with CT head consistent with hydrocephalus) an external ventricular drain will be placed. Most patients will get either a CT angiogram or a conventional angiogram to rule out a vascular malformation, especially if there is no history of trauma. If an aneurysm is detected, the standard of care is to treat it as soon as possible. Usually, an aneurysm iseither coiled or clipped (craniectomy or craniotomy). Every patient admitted with subarachnoid hemorrhage will get graded accordingly to their headache intensity, level of consciousness and neurologic deficits with the Hunt Hess grade (table 2). Their CT scans also get graded (modified fisher scale mFS) according to the thickness and location of blood (table 3). All subarachnoid hemorrhage (unless there is minimal amount of blood and no vascular malformation) are admitted to the Neurosurgical care unit (NSCU). Detailed physical examination, including the NIHSS, history, including medication history, past medical, surgical history, and social history are recorded in the medical records. North Shore University hospital NSCU is the referral center for most of the hospitals in Northwell health care system. Most aneurysmal SAH patients get transferred to our unit. Per standard of care, all women of child bearing age, admitted to the NSCU get a urine or blood pregnancy test, patients suspected of abusing drugs get urine toxicology. Once in the NSCU, patients get vital signs and neurologic assessment every hour, and pain assessment every 4 hours and as needed. The length of stay in the intensive care unit depends on the amount of blood on the head scan (mFS). Patients with higher mFS are more prone to get delayed cerebral ischemia. As a result, per standard of care, patients with SAH get almost daily transcranial dopplers to monitor for cerebral vasospasm, frequent head scans, occasionally brain perfusion studies and MRI of the brain. Patients are monitored for central fever (vital signs, blood cultures), cerebral salt wasting with frequent BMP and urine output measurements, seizures with PRN electroencephalograms (EEG). Once out of the critical care period, (vasospasm usually starts at day 3 post bleeding and peaks at day 10), patients get transferred to a regular neurosurgical floor before being discharged home or to rehabilitation. On average patients stay in the NSCU between 2-21 days. All patients admitted to the NSCU with SAH will be screened and evaluated for the inclusion and exclusion criteria after obtaining an informed consent.

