
Screening involves reviewing the medical records following HIPPA regulation for: Age, gender, ethnicity, presence of aneurysm, day of rupture, etiology of the SAH if not aneurysmal, radiologic (Angiogram, CT head) and medical history before and after the aneurysm is secured, Glasgow coma score before and after aneurysm repair, modified fisher scale (mFS), Hunt-Hess grade (HHS), time of ictus, history of alcohol and drug abuse, presence of hydrocephalus on head CT, presence of an external ventricular drain (EVD), date of EVD placement, new HHS after EVD placement, clipping or coiling. Medical records will be reviewed for the past medical history (pacemaker, defibrillator, history of CHF, arrhythmias, cervical carotid disease, history of a headache disorder like migraine or cluster headache), physical examination, labs will be reviewed which includes but not limited to pregnancy test and urine toxicology. Headache intensity and opiate, steroids and acetaminophen usage are recorded in the electronic medical record. The presence of vasospasm and delayed cerebral ischemia will be noted. Once found eligible satisfying the inclusion and exclusion criteria, and informed consent signed, patients will be randomized to either the treatment group or the control group. The same data will be recorded for both groups. The treatment period will start once admitted in the NSCU and will last for up to 10 days.

During the NSCU stay, patients areevaluated for pain every 4 hours. If vital signs are stable (SBP> 100 mmHg and HR> 60 beats per minutes with no arrhythmia on telemetry, MAP> 60 mmHg and oxygen saturation > 90%) patient will receive either the treatment (nVNS) or the Sham device every 5 hours. Headache intensity will be evaluated every four hours. In addition, vital signs will be noted just after stimulation, and hourly afterwards or as ordered by the physician. The daily mean morphine equivalence dosage will be recorded. Concomitant medications will be recorded.

During the ICU length of stay, the following will be assessed and recorded per standard of care :

- Transcranial dopplers (TCD)
- Neuroimaging (CT head, MRI brain, angiograms, CT perfusion with permeability study)
- EVD weaning and day of start of weaning
- Presence of vasospasm, delayed cerebral ischemia, Central fever, Cerebral salt wasting. These are usually recorded in the medical record.
- Urinary retention documented as frequent straight catheterization for more than 3 days

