9.4.2 ANALYSIS OF THE PRIMARY EFFICACY ENDPOINT(S)

-The difference between the active and sham treatment groups in daily mean morphine equivalence dosage during the study

Repeated measures mixed models will be used to describe the difference between the active and sham treatment groups in morphine equivalence dosage during NSCU length of stay. Morphine equivalence dosage will be modeled as a function of treatment group and measurement time. Subject will be included as a random effect. Least squared means will be used to estimate the treatment effect.

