Title: Safety and efficacy of non-invasive Vagus Nerve Stimulation (nVNS) in the treatment of headache in Subarachnoid Hemorrhage (SAH)

MAY, 1, 2022

NCT04126408

Overview of study design

This is a single site, randomized, sham-controlled, double-blind study assessing the feasibility, safety, tolerability, and efficacy of non-invasive VNS (nVNS) in the treatment of headache in subarachnoid hemorrhage (SAH).

We hypothesize that two two-minute noninvasive stimulations of the cervical branch of the Vagus nerve, every 5 hours, is efficacious in safely reducing headache intensity and frequency in patients with headache due to SAH, during the patient's intensive care unit (ICU) stay.

After screening and obtaining informed consent, eligible patients diagnosed with SAH on head scans, admitted to the Neurosurgical Intensive Care Unit (NSCU) at Northshore University Hospital will be randomized to either the treatment (stimulation of the cervical branch of the Vagus nerve) or sham (inactive stimulation) group.

Pain intensity will be evaluated every 4 hours. Non-invasive stimulation will be performed every 5 hours.

The treatment arms are the following:

Group 1: Control (patients will receive treatment using an inactive VNS device)

Group 2: Treatment (patients will receive treatment using an active VNS device)

The patients are randomized with equal probability to one of the treatment arms. In total, approximately 40 patients will be recruited

Primary objective

The primary objective of this study is to evaluate the effectiveness of VNS compared to sham device as measured by the mean daily morphine equivalence dosage during the study

Secondary Objectives

The secondary objectives of the study are to compare VNS to sham treatment with respect to effects on the following:

- total overall morphine equivalence dosage
- mean daily headache intensity during the study
- cytokines levels
- blood brain permeability markers in the blood and/or CSF before and after stimulation
- blood brain barrier integrity

Exploratory objectives:

- stroke, vasospasm, DCI, seizure, and central fever
 - The presence of DCI,
 - Transcranial doppler velocity,
 - The number of days with central fever,
 - Incidence of seizures
- severity of cerebral vasospasm during DSA

Safety objectives:

- Opiate related adverse events (such as urinary retention, constipation, sedation, nausea, vomiting and pruritis)
- Occurrence of Adverse Events (AEs)/Serious Adverse Events (SAEs)
- Vital Signs

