The primary efficacy variable, the daily morphine equivalency dose by visit, will be analyzed using a restricted maximum likelihood (REML)-based repeated measures approach (Mixed Model Repeated Measures (MMRM)). The model for analysis will include fixed, categorical effects of treatment, visit, and treatment by visit interaction, as well as the continuous, fixed covariates of baseline value. An unstructured (co)variance structure will be used to model the within-patient errors. If this analysis fails to converge, compound symmetry will be tested. The (co)variance structure converging to the best fit, as determined by Akaike's information criterion will be used as the primary analysis. The Kenward-Roger approximation will be used to estimate denominator degrees of freedom. The primary treatment comparison will be the contrast between treatments at Day 14 for active treatment versus sham treatment. Treatment group differences contrasts will be computed overall and for each analysis visit (i.e., Day 1, Day 2, Day 3, ..., Day 14) and displayed with the respective 95% CIs. Significance tests will be based on least-squares means and Type III sum-of-squares, using two-sided tests at the 0.05 level (two-sided 95% confidence intervals). No imputed values will be used for the MMRM analysis.

Sensitivity analysis

All analyses on the primary efficacy endpoint will be repeated on the PPS

Additionally, the missing data for the mean daily morphine equivalency dose will be computed using an LOCF algorithm and analyzed using the MMREM model.

Analysis of Secondary and Exploratory Variables

For each of the variables mentioned above, the randomization group difference will be examined using a T-test for continuous variables, and Fisher's exact test for categorical variables at each visit.

Analysis of safety variables

Treatment group differences in the occurrence of serious adverse events will be evaluated using Fisher's exact test.

Adverse events:

The primary safety endpoint of this study is the overall incidence of device related serious AEs. AEs and SAEs will be summarized and presented as proportions and respective 95% exact binomial confidence intervals (CIs).

Frequency and percentage of subjects experiencing a specific adverse event will be tabulated by system organ class, preferred term, and treatment group.

Summary tables and subject data listings will be provided.

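### Craniotomy, already recorded at screening, is in neither the primary model nor the total-dose analysis; pre-specifying it is a cheap gain in precision, not a correction of bias

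*SAP*

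**What the plan says.** **Primary model.** The SAP (Efficacy Analysis) specifies a REML repeated-measures model with "fixed, categorical effects of treatment, visit, and treatment by visit interaction", "as well as the continuous, fixed covariates of baseline value". Baseline is the Day 1 value (SAP, General approach). Protocol 9.4.2 is sparer: "Morphine equivalence dosage will be modeled as a function of treatment group and measurement time", with a subject random effect and no baseline term.

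**Total dose.** Protocol 9.4.3 uses an ANCOVA adjusted for number of days in the study. The SAP (Analysis of Secondary and Exploratory Variables) uses a t-test. Neither includes baseline dose or procedure.

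**Randomisation.** SAP overview: "The patients are randomized with equal probability to one of the treatment arms" and "In total, approximately 40 patients will be recruited". Protocol 6.3: "Patients will be randomized using variable block design, assigning patients 1:1". No stratification factor is named, and Protocol 4.1 leaves details of the procedure to be worked out after protocol approval.

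**Procedure type.** Protocol 8.1 describes aneurysms as "coiled or clipped (craniectomy or craniotomy"), and its list of screening data includes "new HHS after EVD placement, clipping or coiling". Aneurysm patients join only after treatment (Protocol 5.5). Patients with no vascular malformation on angiogram are also eligible (inclusion criteria).

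**The concern.** The primary endpoint is opioid dose. A clipped patient has just had open cranial surgery; a coiled or angiogram-negative patient has not. If the surgery affects opioid use during the study, procedure mix is a prognostic factor that the plan collects but does not use.

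Two things would follow in a trial of about 40. The arms could differ by chance in the share clipped, which would move the single estimate the pilot produces. The variation between procedure groups would also stay in the residual and widen the interval. Both matter because the pilot's stated purpose is to inform the sample size of a larger trial, and the effect estimate and residual variance feed that calculation.

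The one-day baseline dose may be only a partial substitute. Enrolment can fall anywhere from day 1 to day 5 after aneurysm treatment (Protocol 4.1), so equal baseline doses can come from different points of recovery. The total-dose analysis does not have even that adjustment.

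**Working it through.** The documents give no power, effect size, SD, clipped share or dose by procedure, so there is no plan figure to reproduce. The check uses stated assumptions.

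**Inputs**
- From the documents: about 40 patients, 1:1, so 20 per arm.
- Assumed: clipped share p = 0.3 to 0.5.
- Assumed: g = 0 to 1.0, where g is the clipped-minus-not-clipped difference in follow-up dose left after the model's other adjustments, in residual SDs.
- Assumed low case: 30 patients (15 per arm), because the primary set is the mITT, which requires at least 7 treated days.

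**1. Chance imbalance.** The number clipped in each arm is taken as binomial. A gap of 20 points is 4 patients of 20, or 3 of 15.

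| Per arm | p = 0.3 | p = 0.5 |
|---|---|---|
| 20 | 23% | 27% |
| 15 | 32% | 36% |

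These average over the total number clipped. Fixing the total at exactly 12 or 20 of 40 gives 30% and 34%; neighbouring odd totals give less.

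**2. Shift in the realised estimate.** Shift = imbalance × g. At 20 points this is 0.2 × 0.5 = 0.10 SD, or 0.2 × 1.0 = 0.20 SD. The standard error without the term is 2√(1 + p(1−p)g²)/√40, which is 0.32-0.33 SD at g = 0.5 and 0.35 SD at g = 1.0. The shift is therefore about 0.3 to 0.6 of a standard error.

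**3. Precision.** Partial R² = p(1−p)g² / (1 + p(1−p)g²). With intercept, treatment and one covariate, 40 patients leave 37 degrees of freedom, and 36 with craniotomy added. SE ratio (with/without the term) = √((1 − R²) × 37/36).

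| g | R² | SE ratio |
|---|---|---|
| 0 | 0 | √(37/36) = 1.014 |
| 0.5 | 0.05-0.06 | 0.98-0.99 |
| 0.8 | 0.12-0.14 | 0.94-0.95 |
| 1.0 | 0.17-0.20 | 0.91-0.92 |

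Example at p = 0.5, g = 1.0: R² = 0.25/1.25 = 0.20, and √(0.80 × 37/36) = 0.907. With 30 patients the cost at g = 0 is √(27/26) = 1.02.

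**4. Does the Day 1 dose already do the work?** A single-follow-up ANCOVA was simulated (40 patients, blocks of 2 and 4, 4,000 runs per scenario, true difference 0.8 SD, baseline correlation 0.5 or 0.7). It simplifies the full repeated-measures model.
- Procedure effect of 0.5-1.0 SD equally present at baseline and follow-up: power with and without the term differed by under 2 points.
- Effect of 0.8 SD absent at baseline and present later: omission cost 6-7 points (about 72% against 78% at correlation 0.5).
- Without the term, average bias was nil and type I error was 4.4-5.7% throughout.

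**5. Total dose.** With days in study as the only covariate, the ratios in step 3 apply and no baseline dose absorbs the effect: about 1-2% smaller at g = 0.5 and 5-6% smaller at g = 0.8.

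**The case against.** The case against is substantial, and most of it limits the size of the point.

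- **No documented link to opioid use.** A reader might infer that clipping drives opioid need. The documents say only that it is open cranial surgery; the daily means in Protocol 2.1 (15.7 and 18 mg) have no split by procedure and no SD. The link is plausible but assumed. This stands.
- **The baseline dose is post-procedure.** The study period starts 24 hours after aneurysm treatment and baseline is Day 1, so the model already adjusts for a dose taken after any craniotomy. Step 4 shows that this can absorb nearly all of a constant effect. This stands for the primary model and does not reach total dose.
- **Chance imbalance is not bias.** A reader might infer that imbalance would pass for a device effect. Randomisation and the confidence interval cover it: no average bias and no type I inflation. This stands.
- **One yes/no term does not model a different recovery course.** It adds the same shift at every visit. Procedure-by-visit terms would cost many parameters in this sample. This stands, and it limits the gain at the Day 14 contrast.
- **Other recorded factors could be chosen.** Screening also captures external ventricular drain, Hunt-Hess grade and modified Fisher grade, and the documents do not rank them. Craniotomy is a judgement, made because the endpoint is opioid dose.
- **Stratification is not ruled out.** None is named, but the randomisation details were still to be developed.

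The objection that procedure has three levels does not stand: for craniotomy yes/no, coiled and angiogram-negative patients are both no.

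**Conclusion.** The point holds as a modest improvement in precision. The plan collects a plausible pre-randomisation prognostic factor and uses it in neither analysis. The change in standard error is about +1% to -9% for a remaining effect of 0 to 1 SD, close to nil in the primary model if the Day 1 dose carries the effect, and clearest for total dose. A 20-point imbalance has a 23-27% chance at 20 per arm and 32-36% at 15.

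A reader might hope for a 15% reduction in standard error. That needs R² of 0.30, meaning a remaining effect of about 1.3-1.4 SD after baseline adjustment, which nothing in the documents supports.

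All sizes rest on the assumed clipped share and remaining effect. Baseline-only adjustment is valid as it stands, so this is no threat to the trial's validity.

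**What to change.** - In the SAP's primary model, add craniotomy (yes/no; coiled and angiogram-negative patients as no) as a fixed covariate.
- For total dose, use the protocol's ANCOVA rather than the SAP's t-test, and add the same term. Whether days in study, which is determined after randomisation, belongs in that model is a separate question.
- Tabulate craniotomy by arm with the baseline characteristics. The SAP's planned between-arm comparison names only demographics and vital signs.
- Reconcile Protocol 9.4.2 with the SAP on baseline adjustment in the same edit.

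The cost is a few SAP sentences, no new data, and one degree of freedom: 1.4% on the standard error with 40 patients and about 2% with 30 if procedure has no effect. The total-dose change also replaces the SAP's stated method. The term should be written in before unblinding, since adding it later would look driven by the data.
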